Aim 1: To determine the impact of telephone delivered Problem-Solving Therapy on disability in GWV with GWI. H1: Among Veterans with GWI, telephone delivered Problem-Solving Therapy will produce greater improvement in disability as compared to telephone delivered health education.

Aim 2: To determine the effect of Problem-Solving Therapy on problem-solving ability in GWV with GWI. H2a & H2b: Among Veterans with GWI, telephone delivered Problem-Solving Therapy will produce greater improvement in (H2a) self-reported problem-solving ability (measured with the Problem-Solving Inventory) and (H2b) objective problem-solving ability (measured with a neuropsychological battery) as compared to telephone delivered health education.

H2c & H2d: Improvement in (H2c) self-report problem-solving ability and (H2d) objective problem-solving ability will mediate the effect of telephone delivered Problem Solving Therapy on disability.

Exploratory Aim 3: To determine the effect of Problem-Solving Therapy on other symptoms of GWI. Problem-Solving Therapy may help GWV with GWI better compensate for other symptoms (e.g. avoid over exertion) which may improve other symptoms of GWI.

Exploratory H3a – H3b Among Veterans with GWI, telephone delivered Problem-Solving Therapy will produce greater improvement in (H3a) self-reported pain and (H3b) fatigue as compared to telephone delivered health education.

Study Population

We will screen up to 2,000 Veterans to obtain a final sample of up to 300 Veterans from the Gulf War who screen positive for GWI.

Inclusion:

- (a) deployed to first Gulf War and meets Kansas definition for GWI (see definition in measures section);
- (b) scores at least a half a standard deviation worse than the mean on the World Health Organization Disability Schedule (WHO-DAS II).

Exclusion:

- (a) current suicidal/homicide intent or plan assessed by The Columbia Suicide Severity Rating Scale, schizophrenia or current psychotic symptoms
- (b) self-reported diagnosis of a degenerative brain disorder or serious psychiatric or medical illness which may limit generalizability of the findings, limit safety or account for the symptoms of GWI.

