Once potential participants are identified, introduction letters will be mailed to their addresses. Approximately after two weeks of mailing the introduction letter to Veterans, research staff will contact potential participants to inform them about the study, obtain verbal consent for and conduct initial screenings over the phone. For Veterans who contact us over the phone or in-person, (e.g., after reading a posted flyer), we will obtain verbal consent for and conduct initial screenings in person or over the phone.

If a Veteran is screened as eligible to participate in the study, a date and time will be scheduled for the Veteran to come into one of the three study sites (East Orange VA, Canandaigua VA or Bedford VA) to be consented into the study and complete the baseline questionnaires and neuropsychological assessments.

b. Sessions

Once consented and baseline assessments (described below) are completed, therapy sessions will be scheduled with a Study Provider from the East Orange VA. Study providers will be a licensed provider, e.g., psychologist, nurse, social worker, or a trainee e.g., working under a licensed provider, at the East Orange VA. A Study Provider from the East Orange VA will provide the sessions via phone with all participants from all VA sites (East Orange VA, Canandaigua VA, and Bedford VA). We will have a standardized assessment regimen that all Study Providers will adhere to. Therapy sessions will be scheduled weekly, and may be adjusted to accommodate the Veteran's schedule and/or needs.

The telephone sessions with the Study Provider will generally be 1 hour. Most telephone sessions will be voice recorded and transcribed for quality assurance, i.e., fidelity to study protocols, length of sessions, engagement of participants. Coding of telephone sessions will occur by our off site collaborators once proper approvals are in place (i.e., DUA).

Study Arms

Veterans will be randomized either to the PST (treatment) or Health Education group (control).

If randomized to the PST (treatment):

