11. Behavioral Responses to Illness Questionnaire (BRIQ): The BRIQ was developed to assess how individuals problem-solve medically unexplained symptoms. Internal reliability is above .80, test-re-test reliability is acceptable (.60-.87) and it is able to predict the onset of medically unexplained symptoms (Spence et al., 2005).
12. Demographic Survey & Healthcare Access: This is a brief questionnaire designed to elicit basic demographic information including: sex, age, marital status, self-identified racial and ethnicity group, educational level, income level, sources of current income, and current employment status, health insurance and health care utilization. The information obtained through this survey will be used to assess demographic differences between groups and identify potential control variables. We will also ask for self-report of medical conditions and medication.
13. The Brief Traumatic Brain Injury Screen (BTBIS): The VA/DOD BTBIS assesses TBI by asking if the participant has had an injury and if the injury resulted in a symptom. It will be used as a control variable in analyses.
14. Patient Health Questionnaire (PHQ-8): The PHQ is a self-administered questionnaire yielding algorithmic diagnoses of psychiatric illness. It was specifically developed and validated for use in primary care settings. We will administer the 8 item depression questionnaire. Patients are instructed to code each symptom based on whether it bothered them over the preceding 2 weeks: “not at all”, “several days”, “more than half the days”; or “nearly every day”. Depression is a common comorbid condition among Gulf War Veterans with Gulf War Illness.
15. Post Traumatic Stress Disorder Checklist (PCL): The 21 item National Center for PTSD Checklist of the VA will be used to assess PTSD. When compared to the gold standard for assessing PTSD, the Clinician Administered PTSD scale (CAPS), the PCL has been shown to be a valid and reliable measure of PTSD symptoms. PTSD is a common comorbid condition among Gulf War Veterans with Gulf War Illness.
16. Alcohol Use Disorders Identification Test (AUDIT-C): a 4-item alcohol screen used to identify patients with hazardous drinkers or have alcohol use disorders. The AUDIT is used in the VA to screen patients with alcohol use disorders.

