Data analyses will be conducted both on-site by study investigators and with proper approvals, including DUAs, at our affiliate institutes by current and future study investigators. All analyses will be primarily performed on an intention-to-treat basis. The statistical significance will be defined by a p value < 0.05 , unless specified otherwise. Calculations of the means, standard deviations, proportions, histograms, etc., will be conducted to explore the distributions of the data, identify outliers, and calculate correlations between variables. We will also determine confounders that need to be controlled for in our analyses. We will particularly examine if we need to control for depression measured with the PHQ-8 or PTSD symptoms measured with the PCL based characteristics that exhibit differences at the baseline (pre-intervention).

Due to repeated measures, we will analyze the data using mixed model analysis, with participants nested within therapists modeled by random effects. To address H1, disability (WHODAS II scores) will be treated as the dependent variable, and treatment assignment [PST vs. Health education], time [pre- vs. post-intervention] and their interaction will be modeled as fixed effects. Differences in the improvement of disability between Problem-solving therapy and Health education will be evaluated by the treatment by time interaction. Linear contrasts will be constructed to evaluate the improvement in disability for each treatment separately. Variables such as age, gender, education and the confounders identified in the preliminary analysis will be controlled as covariates in the statistical analyses. Data transformations (e.g., square root, log,

etc.) will be used to normalize data where necessary. The same mixed model analysis strategy will be applied to address H2a, H2b, H3a and H3b. We will also explore, using this same mixed model strategy, the impact of PST therapy on each of the four individual neuropsychological tests scored as a composite and scored individually (Category Test, CPT 3, Stroop Test, and TMT). We will use the same data analysis strategy to examine all secondary outcomes. These will be reported as secondary outcomes and will primarily be used to generate hypotheses.

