To address the H2c and H2d, we will establish a mediational model to explore whether the PST produces greater improvement in disability through its effects on problem-solving ability (measured by either the self-report (H2c) or the objective measurements (H2d)), following the recommendations of Baron and Kenny. The same mediational model will be used to explore whether participants views of treatment (e.g., relationship with therapist) also mediates the relationship between PST and disability. The statistical analysis will be performed using the mixed model analysis. Using these general methods we will also examine the impact of the treatment on other outcomes of interest, the relationship between variables and other potential moderators and mediators; we will also explore the relationship between variables of interest assessed concurrently.

b. Qualitative Data

Qualitative interviews will be transcribed and analyzed using standard qualitative research methods. The data to be analyzed are the participants' own words and narratives. Several members of the study team will perform an initial independent read through of interview notes and transcripts and generate a list of domains to create the initial coding scheme. Initial domains are expected to parallel the major themes or questions in the discussion and interview guides. Initial codes will be used to inform ongoing interviews and coding schemes. Once codes have been finalized, the coding scheme, interview notes and transcripts for interviews will be entered into an Excel or a qualitative software package. Study team members will apply the codes and labels to text.

Risks and Benefits

Risks

The risks of this study include:

1. Loss of confidentiality
2. Emotional distress. Some Veterans could find some of the questionnaires and the phone sessions upsetting.

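### For the mediation hypotheses H2c and H2d, the only stated criterion for adjusting for depression or PTSD is a baseline difference, which does not address mediator-outcome confounding; false mediation is possible for H2c

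*Combined protocol and SAP*

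**What the plan says.** Aim 2 states, as H2c and H2d, that improvement in self-reported and in objective problem-solving "will mediate the effect of telephone delivered Problem Solving Therapy on disability". These are hypotheses of Aim 2, not of the exploratory Aim 3, although Data Analysis, a. Data, speaks of exploring: "we will establish a mediational model to explore whether the PST produces greater improvement in disability through its effects on problem-solving ability". The method is described as "following the recommendations of Baron and Kenny", fitted by mixed models. The mediation paragraph names no covariates, no assumption about common causes of mediator and outcome, and no sensitivity analysis.

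Covariates are dealt with earlier in the same section. There is a general promise to determine confounders, next to a step that calculates correlations. Age, gender, education and the identified confounders are then to be controlled. On depression and PTSD, the plan will examine whether control is needed for PHQ-8 "or PTSD symptoms measured with the PCL based characteristics that exhibit differences at the baseline (pre-intervention"). That sentence is garbled; a difference between arms is its natural reading.

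Elsewhere, the TBI screen is named as a control variable (b. Questionnaires, item 13), and adherence and alternate treatments are to be controlled for (Reducing Attrition). Item 14 of the questionnaires says: "Depression is a common comorbid condition among Gulf War Veterans with Gulf War Illness". Item 15 says the same of PTSD.

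**The concern.** Randomisation protects two of the three mediation paths: PST to problem-solving, and PST to disability. It does not protect the path from problem-solving to disability, because nobody is randomised to a PSI score. That path is interpretable only if the variables that drive both scores are in the model.

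A baseline-difference criterion asks another question, namely whether the arms happen to differ. Depression can be perfectly balanced between arms and still worsen both the self-rated PSI and the self-rated WHO-DAS. The criterion will then usually leave it out of the model that needs it.

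At stake is the trial's claim about mechanism. A PST effect on disability that bypasses problem-solving could be reported as working through it. The H1 comparison of arms is not affected.

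**Working it through.** The plan gives no power calculation, correlation or mediation error rate, so there is no figure of its own to reproduce.

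**Inputs from the documents.** Significance: "The statistical significance will be defined by a p value < 0.05" (two-sided assumed). Size: "a final sample of up to 300 Veterans from the Gulf War". Allocation: "Veterans will be randomized either to the PST (treatment) or Health Education group (control"); the ratio is not stated, so 1:1 and 150 per arm are assumed.

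**Assumed inputs.** The true PSI-to-WHO-DAS path is zero. PST shifts each score by 0.4 SD. Each score has variance 1, of which 0.7 is stable and 0.3 is occasion noise. A stable depression trait loads λ = 0.3, 0.4 or 0.5 on both scores. False mediation means that the total effect, the PST-to-PSI path and the PSI-to-WHO-DAS path are all significant and the direct effect is smaller than the total effect.

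**Step 1: how often the criterion selects depression or PTSD.** Tested between randomised arms at p<0.05: 5% each. For at least one of two independent covariates: 1 − 0.95² = 9.75%. Neither figure depends on how strongly the covariate confounds.

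**Step 2: the first two paths.** The shift divided by its standard error is 0.4 / √(2 × 0.6 / 150) = 0.4 / 0.089 = 4.5, so both are almost always significant. The third path decides.

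**Step 3: two-visit random-intercept model with raw PSI as covariate.**
- Weighted information per person on PSI: within-person 0.3/0.3 = 1, plus person mean 1.7/1.7 = 1.
- The PSI-WHO-DAS cross-product sits only in the person mean: 2λ²/1.7.
- Spurious path b = (2λ²/1.7)/2 = λ²/1.7. Standard error ≈ 1/√(2 × 300) = 0.041.
- P(b significant) comes from the normal distribution. Under the criterion the rate is 0.95 × P + 0.05 × 0.05.

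| λ | b | b/SE | P(b significant) | With criterion, formula | All steps, simulated |
|---|---|---|---|---|---|
| 0.3 | 0.053 | 1.30 | 25% | 24% | 25% |
| 0.4 | 0.094 | 2.31 | 64% | 61% | 62% |
| 0.5 | 0.147 | 3.60 | 95% | 90% | 90% |

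With depression always in the model, simulated false mediation is about 3%. At 110 per arm the criterion gives 19%, 46% and 79%.

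**Step 4: post scores adjusted for baseline PSI and WHO-DAS, depression left out.** Let e₊ = 0.3(0.7+λ²)/(1+λ²) and e₋ = 0.3(0.7−λ²)/(1−λ²). Then b = [(e₊−e₋)/2] / [(e₊+e₋)/2 + 0.3]. At λ = 0.5: e₊ = 0.228, e₋ = 0.180, b = 0.024/0.504 = 0.048, and b√300 = 0.82, which gives 13%. Simulated false mediation for the three loadings is 5%, 8% and 13%.

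**Step 5: change on change, depression left out.** The covariance of the two changes is λ² − λ² − λ² + λ² = 0, so b = 0. False mediation is 2% to 3%. That is the floor, since b must be significant in the one direction that shrinks the direct effect (half of 5%).

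**Step 6: when the confounder is not a constant trait.** Here the baseline confounder correlates k with the mediator and l with the outcome, each taken as follow-up score or change. PST effects are 0.5 SD, N = 300, and ordinary regression is used. The spurious path is k × l. False mediation under the criterion is 9% (0.2/0.2), 32% (0.3/0.3), 69% (0.3/0.5) and 93% (0.5/0.5), against about 2% with the confounder always included. If the common cause arises after baseline (0.3/0.5), always adjusting for the baseline value leaves the rate at 73%.

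**Step 7: conditions.** With 0.3/0.5 and no PST effect on the mediator, the rate is 1.4%. With no total effect it is 1.5%. With both effects at 0.3 SD it is 39%.

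**The case against.** The strongest reply has four parts.

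- **The plan does control for confounders.** It has a general confounder step, calculated correlations, age, gender, education, TBI, and adherence and alternate treatments, and it names depression and PTSD as candidates. This stands against a reader who infers that the mediation models have no control at all, or that depression and PTSD cannot be found. They can enter by chance or through the open confounder step. But no rule links the correlations to the choice of covariates, and the one criterion stated for depression and PTSD is the baseline difference.
- **The hypotheses concern improvement, and a stable trait cancels in change scores.** This is correct (Step 5). But the plan names mixed models and does not give the form of mediator and outcome. A random-intercept model also uses differences between persons, and a confounder that acts on change brings the bias back. Baseline disability would enter a pre-post mixed model as a repeated outcome, but Step 3 shows that this does not remove the bias.
- **The criterion is garbled and has no stated test.** True. The between-arm reading and the 5% figure are interpretations.
- **Only self-report was examined.** True. A reader might extend the figures to H2d, but its mediator is objective testing. It was not simulated, and the documents give nothing on how depression relates to those tests.

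**Conclusion.** The concern holds in a limited form. The stated criterion for depression and PTSD detects chance imbalance between arms, not variables that drive both problem-solving and disability, and the mediation paragraph adds no other prespecified protection.

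For H2c, false mediation can be declared if PST moves both PSI and WHO-DAS and depression worsens both. The size depends mainly on a model form that the plan leaves open: from no inflation (change on change, stable confounder), through 5% to 13% (baseline-adjusted post scores), to 25% to 90% (random intercept with raw PSI). Every loading, effect size and variance share is assumed. A reader might take the upper figures as the plan's expected error rate; the documents support only the range and its conditions. For H2d the same gap in the text exists, but no size can be given.

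**What to change.** Add to the mediation paragraph of Data Analysis, a. Data:

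- The H2c and H2d outcome models use post scores modelled on baseline. They always include baseline PHQ-8, baseline PCL-5, the baseline value of the mediator and baseline WHO-DAS, whatever the balance between arms.
- The baseline-difference criterion does not apply to H2c and H2d.
- A sensitivity analysis reports how strong a remaining mediator-outcome correlation would have to be to bring the mediated effect to zero. This is needed because baseline adjustment cannot remove confounding that arises later (Step 6).

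The Summary List of Measures and Timeline shows the four questionnaires at baseline, and the neuropsychological tests for H2d are also given then. No new data are needed. The cost is a few sentences, a little more analysis work, and mediated effects that may come out slightly smaller.

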Qualitative assessments and interviews may be recorded, transcribed, and coded for further data analyses. Personal identifiers will not generally be transcribed from the voice recordings.

Additionally, we will review participants' medical records and collect information on previous and future medical treatment including physical and mental health treatment, diagnoses and medication.

c. Neuropsychological Measures

These measures capture Problem-solving Ability or Executive Function. These measures will be administered in-person at the baseline assessment visit and after the 12th session assessment visit. Problem-solving, an executive function refers to the ability of an individual experiencing an undesirable situation to move to a more desirable one when no response is immediately apparent or available. Problem-solving is considered the most complex of all cognitive functions as it requires the use and integration of other cognitive functions like attention, processing speed, effort, and impulse control as well as other executive functioning skills like mental flexibility and abstract thinking. Neuropsychological testing can be used to measure participants' functioning in the entire range of cognitive skills that problem-solving demands. We propose to use 5 neuropsychological instruments to measure functioning in the following cognitive areas: Attention, processing speed, impulse control, effort, mental flexibility and abstract thinking.

1. Halstead Category Test, Russell Revised Version: The Category Test is an objective test of problem-solving ability, specifically abstract thinking and mental flexibility. The test takes 30-40 minutes to administer. Our previous work has shown that the Category Test is able to differentiate Veterans with GWI from Gulf War Veterans without GWI. The Category Test has acceptable test-retest reliability and has been used as an outcome in cognitive rehabilitation treatments.
2. The Conner's Continuous Performance Test-3 (CPT-3): The CPT-3 is a measure of ability to alternate attention, inhibit impulses and mental flexibility. The CPT-3 is a valid and reliable measure that and this version includes norms for adults with brain disorders as well as attentional disorders. It can and has been used in treatment efficacy trials.

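### H2c and H2d rest on Baron-Kenny steps with no estimate or interval for the indirect effect and no named mediator or outcome visit, which can cost power and leaves direction open.

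*Combined protocol and SAP*

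**What the plan says.** Aim 2 states the hypotheses: "Improvement in (H2c) self-report problem-solving ability and (H2d) objective problem-solving ability will mediate the effect of telephone delivered Problem Solving Therapy on disability". Only Aim 3 is labelled exploratory.

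Under Data Analysis, a. Data, the mediation model is meant to "explore whether the PST produces greater improvement in disability through its effects on problem-solving ability", "following the recommendations of Baron and Kenny". On the model itself the text says only: "The statistical analysis will be performed using the mixed model analysis". The steps are not written out, and no test or interval for the indirect effect is given. No visit is named for the mediator or the outcome.

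The only time factor in the section belongs to the H1 model, which is reused for H2a, H2b, H3a and H3b: "time [pre- vs. post-intervention] and their interaction will be modeled as fixed effects".

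The Summary List of Measures and Timeline marks the PSI and the 36-item WHO-DAS at baseline, week 4, week 12 and 6 months. For the neuropsychological battery, Assessment Instruments, c. Neuropsychological Measures, says: "These measures will be administered in-person at the baseline assessment visit and after the 12th session assessment visit".

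**The concern.** Two separate things are at stake.

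- **Power.** Classical causal steps infers mediation from a pattern of separate significance tests, the first being the total effect of treatment on outcome. Here that first test is H1, so the power for H2c and H2d cannot exceed the power for H1. The indirect effect, which is the quantity the hypotheses are about, gets neither an estimate nor a measure of precision.
- **Direction.** If mediator and outcome come from the same visit, three explanations fit a positive result: better problem-solving reduced disability, reduced disability improved problem-solving, or a common cause moved both. For H2c both measures are self-reported, so the reverse path is easy to imagine. For the objective battery in H2d it is less obvious, but a common cause remains possible.

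Because no visits are named, the choice could also be made after the data are seen.

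**Working it through.** The plan has no power figure for mediation to reproduce, so every effect size below is an assumption.

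**Inputs from the protocol.** Sample: "We will screen up to 2,000 Veterans to obtain a final sample of up to 300 Veterans" (Study Population); 300 is used, with 1:1 allocation assumed. Significance level 0.05 (Data Analysis); two-sided testing assumed.

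**Assumed model.** Mediator M = a·X + error. Disability Y = c′·X + b·M + error. X is the arm, residual SDs are 1, a = 0.4 and b = 0.3. The direct effect c′ runs from 0 to 0.3.

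**Step 1: the two paths of the indirect effect.**
- a: SE = 2/√300 = 0.1155; z = 0.4/0.1155 = 3.46; power = Φ(3.46 − 1.96) = 93%.
- b: SE ≈ 1/√300 = 0.0577; z = 0.3/0.0577 = 5.20; power above 99%.
- Detecting both: about 93%, whatever c′ is.

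**Step 2: the total effect required by causal steps.** Total = a·b + c′ = 0.12 + c′. The SD of Y within an arm is √(1 + 0.3²) = 1.044, so SE = 1.044 × 2/√300 = 0.1206. Power = Φ(total/0.1206 − 1.96).

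**Step 3: all steps together, by simulation** (total effect, a and b each p < 0.05).

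| Direct effect c′ | Total effect | Power of total-effect step (formula) | Causal steps (simulated) | Interval on a·b (simulated) |
|---|---|---|---|---|
| 0 | 0.12 | 17% | 16% | 94% |
| 0.1 | 0.22 | 45% | 42% | 92–94% |
| 0.2 | 0.32 | 76% | 71% | 93% |
| 0.3 | 0.42 | 94% | 87% | 92% |

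**Step 4: sensitivity of the power result.**
- Smaller N matters for H2d because participants may skip the battery. At N = 200, causal steps gives 11%, 50% and 66% at c′ = 0, 0.2 and 0.3, against 78–80% for joint significance of a and b.
- With baseline adjustment (assumed baseline-to-follow-up correlation 0.6) and N = 300, the comparison is 24% v 99% at c′ = 0 and 67% v 99% at c′ = 0.1.
- Over a wider grid at N = 300 (a from 0.2 to 0.8, b of 0.3 or 0.5, c′ of 0, 0.2 or 0.3), causal steps was below 50% in 12 of 30 settings. At a = 0.2 the joint test was itself only 38–41%, so much of that loss is due to effect size and not to the method.

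**Step 5: direction with same-visit data.** With no mediator-to-disability path and N = 300:
- Reverse causation (arm effect on disability 0.3–0.5 SD, disability-to-mediator slope 0.3–0.7) gave a positive causal-steps result in 10–70% of trials.
- An unmeasured common cause (arm effects 0.3–0.5 SD) gave one in 52–99%.
- Joint significance of a and b was at least as often positive, so changing the test does not cure this.

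**Step 6: does lagging cure it?** This was simulated with disability driving the mediator and no path back. Pairing the week-12 mediator with 6-month WHO-DAS, adjusted for baseline values only, was falsely positive in 11–57% of trials, against 16–58% for same-visit data. The reason is that week-12 WHO-DAS drives both the week-12 mediator and the 6-month WHO-DAS. Adding week-12 WHO-DAS to the model reduced the rate to 1–3%.

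The simulations ignore therapist clustering and missing data.

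**The case against.** **The hypotheses presuppose an effect.** H2c and H2d speak of mediating the effect of PST on disability, so asking for that effect first fits their wording. With c′ = 0 the low figure is almost entirely low H1 power (17% against 16%), in a trial that would usually miss its primary hypothesis. This is fair, and it is why the total effect should be reported beside the indirect one. It does not justify withholding an estimate and interval for the quantity hypothesised.

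**A direct path is plausible.** Under Study Arms, providers first help participants increase chosen activities and only then teach problem-solving; Risks calls increased activity a standard component of such treatments. WHO-DAS covers activity and participation. This stands: the c′ = 0 row should not be read as the expected case. Against it, Background presents compensation for problem-solving deficits as the way PST reduces disability.

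**Stronger readings.** A reader might infer that a true indirect effect will usually be missed. The documents give no effect sizes to support that, and with c′ of 0.2–0.3 and a of at least 0.4, causal steps reached 72–100% at N = 300. A reader might also infer that the plan commits to same-visit pairs. It does not: the pre/post factor is written for the other hypotheses, and for mediation no visits are stated. Nor does the trial lack ordered data, since the schedule supplies it.

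**Consequence.** The analysis text describes the mediation work as exploring, and the primary treatment comparison is untouched. That limits the seriousness, although the hypotheses sit under a non-exploratory aim.

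**Conclusion.** The point holds as a weakness worth correcting in the secondary, mechanistic analysis. The plan names causal steps and provides no estimate or interval for the indirect effect and no visits.

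The power loss applies if the total-effect step is enforced, which the plan implies by naming the method but does not write out. Under the assumed paths at 300 participants, the shortfall against an interval on the indirect effect is about 78 percentage points with no direct effect (94 − 16), 22 at 0.2 (93 − 71) and 5 at 0.3 (92 − 87). It is therefore large only when the direct effect is small.

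The direction problem applies if mediator and outcome come from the same visit, which is an inference from the pre/post model. A reader might infer that a lagged pair settles direction. It does not when adjusted for baseline values alone, and unmeasured common causes remain in any version.

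**What to change.** Replace the method sentence for H2c and H2d with the following.

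1. **Main mediation analysis.** Estimate the indirect effect as the product of coefficients with a bootstrap or Monte Carlo 95% interval, adjusted for baseline mediator and baseline WHO-DAS. Report it whether or not H1 is significant, beside the total effect. Name the mediator and outcome visits in advance.
2. **Supporting lagged analysis, from data already scheduled.** Use week-12 PSI (H2c) or week-12 neuropsychological score (H2d) with 6-month WHO-DAS. For H2c add week-4 PSI with week-12 WHO-DAS. Run each with and without adjustment for WHO-DAS at the mediator visit.
3. **Limits.** State that mediator-outcome confounding remains possible, and add a sensitivity analysis for it.

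The cost is SAP wording and some analysis time; no visit or instrument is added. There are three downsides. The analyses with 6-month WHO-DAS use only participants retained to 6 months. Adjusting for WHO-DAS at the mediator visit captures only the later part of any mediated effect. Week 4 falls early in a programme that begins with activity, so the week-4 PSI may show little change.
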